3 INVESTIGATIONAL PLAN

3.1 General Schema of Study Design

This randomized, single-blinded, intervention study will take place at the CHOP outpatient CTSC and at Children's National Medical Center. Subjects with Down syndrome and subclinical hypothyroidism (TSH: 5-10 mIU/L) ages 8-20 years will be recruited for a trial of levothyroxine treatment, using a switching replication design. All subjects will be observed for 6 months. TSH and T4 will be obtained at the 3rd and 6th month of the observation period. If a subject has a TSH which has reverted to normal at 3 months, they will continue on to the 6-month check. Only subjects with persistently elevated TSH (5-10 mIU/mL) at 6 months will be enrolled in the randomized phase. While there is no standard definition of "persistently elevated," in this study, we consider TSH level that is 5-10 mIU/L at 0 and 6 months as "persistently elevated." If TSH is < 5 mIU/L at 0 months and the subject has a history of TSH 5-10 mIU/L, a repeat TSH may be drawn, at the discretion of the principle investigator, within 3-6 months; if TSH is < 5 mIU/mL at 6 months, a repeat TSH may be drawn, at the discretion of the investigator, within 1-2 weeks. If the repeat TSH is < 5 mIU/L, the subject will not be eligible to continue. If TSH is > 10 mIU/L during the first 6 months, a repeat TSH will be drawn within 1-2 weeks. If the repeat TSH is > 10 mIU/L, thyroid dysfunction will not be considered subclinical. The subject will be referred to an endocrinologist for definitive therapy. After 6 months of observation, subjects will be randomized to: Group 1 (6 months of placebo, followed by 6 months of levothyroxine) or Group 2 (12 months of levothyroxine). The initial levothyroxine dose will be 0.5 – 1 mcg/kg/day, with a goal of TSH desired range of 0.5 – 3 mIU/L. Subjects/families will be blinded to the treatment arm. Investigators will be unblinded to permit titration of levothyroxine dose. TSH and T4 will be measured after 6 weeks (month 7.5) of levothyroxine/placebo commencement (as a measure of efficacy of levothyroxine dose), and then at month 12. At month 12, levothyroxine will be initiated in Group 1 (delayed treatment), allowing for 6 months of treatment. Group 2 (immediate treatment) will continue an additional 6 months of levothyroxine (12 months total). TSH will be checked at 6 weeks (month 13.5) and at month 18 in both groups. Dose adjustments will be made at the discretion of the PI. TSH will be repeated 6 weeks after any dose adjustments, which may be in addition to the time points above if necessary. This switching replication design will permit using each child to serve as his/her own control and provides a placebo control period for each treated child. The goal is for 20 subjects to complete the 18 month study.

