3.1.2 Observation Phase

The first 6 months of the study are the Observation Phase of the study. Only subjects with persistently elevated TSH during the Observation Phase will proceed to the Treatment Phase. Subjects that have TSH >10 mIU/L during the 6 month Observational Phase will have a repeat TSH test within 1-2 weeks. If the repeat TSH is >10 mIU/mL, the subject not be considered to have subclinical hypothyroidism and will not qualify to continue the study. They will be referred to an endocrinologist for treatment. Subjects who have TSH <5 mIU/L at the 6 month visit may have a repeat TSH test within 1-2 weeks; this will be at the discretion of the study investigator. If TSH or repeat TSH (if applicable) is <5 mIU/L, the subject will be considered to have normal levels of TSH and will not qualify to continue the study. Subjects who have a history of subclinical hypothyroidism, but at the 0 month visit have a TSH value in the normal range, may have a repeat TSH test within 3-6 months; this will also be at the discretion of the study investigator.

Study Visit #1 (0 Month):- For subjects recruited from #9233, #9233 data will serve as Study Visit #1 data. Study visit #1 will not be necessary for subjects recruited from #9233.

Subjects who have not participated in Study #9233 will complete Study Visit #1. Subjects and their parents/guardians will come to the research facility following a 12 hour overnight fast. Parental/guardian/Legal Authorized Representative consent and child assent (if child is deemed capable of assent) will be obtained prior to any study procedures being performed. Females will receive a urine pregnancy test. Females found to be pregnant will be disqualified from the study and will receive appropriate counseling and referral. Study participants will have the following measures: fasting blood samples, TSH, T4, anthropometric measurements, whole body DXA scan, blood pressure, pubertal assessment, pulse wave velocity & pulse wave analysis, echocardiography and questionnaire assessments. After the study visit, subjects will be asked to wear a physical activity arm band at home for 7 days, and a 3 day dietary recall will be done by telephone.

Blood Draw Visit A(3 Month):- During this observation time frame, subjects will have a blood draw to check TSH and T4 levels. This blood draw can be done at the research facility or at other hospital-affiliated sites.

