The study team will review potential side effects and toxicities with subjects by telephone 4 weeks after treatment initiation. If symptoms are present, TSH and T4 will be checked and dose adjustments made if necessary. If symptoms are absent, TSH and T4 will be checked as scheduled and symptoms reviewed at 6 weeks. All symptoms will be recorded. The Investigative team will have immediate access to TSH and T4 when these data are available from the lab. Thyroid function data will also be reviewed monthly by the study team, to assess study dosing practice.

For subjects enrolled in this study, any subject who develops TSH > 10 mIU/L during the course of the study will have a repeat TSH test done within 1-2 weeks. If the repeat TSH remains > 10 mIU/mL, the subject will be withdrawn from the study and referred to endocrinology for management of hypothyroidism. If a suppressed TSH (TSH < 0.1 mIU/L) is identified in a child on placebo, the TSH will be repeated within 2-3 weeks. If the TSH remains suppressed the subject will be referred to endocrinology for management of possible hyperthyroidism. If a suppressed TSH (TSH < 0.1 mIU/L) is identified in a child on levothyroxine, the levothyroxine dose will be decreased and the lab repeated within 4-6 weeks. If the TSH remains suppressed or child has symptoms consistent with hyperthyroidism, the TSH will be discontinued and the TSH repeated in 6 weeks. If the TSH remains suppressed the subject will be referred to endocrinology for management of possible hyperthyroidism,

At the completion of the study, serum TSH and T4 will be measured, thyroid hormone replacement will be discontinued, and thyroid hormone results from the study reported to the PMD. The subject will be directed to follow-up with the primary care provider or with pediatric endocrinology to determine if continued thyroid hormone replacement is appropriate.

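### Several TSH decision limits, including the on-study withdrawal limit in section 9.4.2, are printed in mIU/mL where mIU/L is meant

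*Combined protocol and SAP*

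**What the plan says.** Most TSH limits in the combined protocol and SAP are in mIU/L. These include the inclusion range (Synopsis and 3.4.1), the titration target (1.4 and 3.1) and the triggers for a repeat test above 10 (3.1, 3.1.2, 9.4.2 and 9.4.3). The suppression limit is too: "If a suppressed TSH (TSH < 0.1 mIU/L) is identified in a child on levothyroxine". Section 3.1 defines persistent elevation in the same unit: "we consider TSH level that is 5-10 mIU/L at 0 and 6 months".

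Four rules depart from this in at least one place.

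- **On-study withdrawal (9.4.2).** The trigger is "any subject who develops TSH > 10 mIU/L during the course of the study will have a repeat TSH test". The action step in the following sentence is "If the repeat TSH remains > 10 mIU/mL, the subject will be withdrawn from the study".
- **Observation-phase repeat above 10.** Section 3.1 has "If the repeat TSH is > 10 mIU/L, thyroid dysfunction will not be considered subclinical". Sections 3.1.2 and 9.4.3 state the same rule per mL.
- **Randomisation gate at 6 months.** Section 3.1 has "Only subjects with persistently elevated TSH (5-10 mIU/mL) at 6 months will be enrolled in the randomized phase". The Synopsis, 3.1.3, 4.3.1, 6.3 and 9.1.1 also print the gate per mL, and 9.1.1 gives only a lower limit of 5.
- **Re-test below 5 at 6 months.** Section 3.1 has "if TSH is < 5 mIU/mL at 6 months, a repeat TSH may be drawn", while 3.1.2 has "Subjects who have TSH <5 mIU/L at the 6 month visit may have a repeat TSH test within 1-2 weeks".

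Two further per-mL entries are descriptive: the expected TSH range in 6.1.1, where the unit is also misspelt as mUI/mL, and the description of subclinical disease in 9.4.3.

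**The concern.** These limits decide which children are randomised, re-tested, withdrawn and referred. The two units differ by a factor of 1000, so the same number cannot be right in both.

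The withdrawal step matters most. It is the only rule for withdrawal and referral at TSH above 10 that covers the treatment phase, and it applies to children on placebo as well as on levothyroxine. Its trigger and its action use different units in consecutive sentences, and no correctly printed version of the action step appears elsewhere. A reader can check the other three rules against 3.1 or 3.1.2.

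**Working it through.** **Conversion.** 1 L = 1000 mL, so x mIU/mL = 1000x mIU/L.

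- Withdrawal step (9.4.2): 10 mIU/mL × 1000 = 10,000 mIU/L. Its trigger is 10 mIU/L, and 10,000 / 10 = 1000.
- Randomisation gate (3.1 and elsewhere): 5–10 mIU/mL = 5,000–10,000 mIU/L, against a defined 5–10 mIU/L.
- Plausibility: the highest TSH cited in the document is 18.9 mIU/L (1.3.2.3 and 1.5). In the other unit this is 18.9 / 1000 = 0.0189 mIU/mL, far below either printed limit.

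**Count of per-mL entries.**

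| Rule | Printed per mL in | Entries | Correct unit in |
|---|---|---|---|
| On-study withdrawal above 10 | 9.4.2 | 1 | nowhere |
| Observation-phase repeat above 10 | 3.1.2, 9.4.3 | 2 | 3.1 |
| 6-month randomisation gate | Synopsis, 3.1, 3.1.3, 4.3.1, 6.3, 9.1.1 | 6 | definition in 3.1 |
| 6-month re-test below 5 | 3.1 | 1 | 3.1.2 |
| Descriptive only | 6.1.1, 9.4.3 | 2 | not applicable |

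Total: 1 + 2 + 6 + 1 + 2 = 12 entries in ten places. The inclusion criterion in 3.4.1 is in mIU/L, but it governs entry. For the 6-month gate, the correct reference is the definition in 3.1.

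**Which unit is meant.**

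1. In 9.4.2 the repeat value must *remain* above the limit. A value can only remain above a limit that it has already passed, and the limit just passed is 10 mIU/L.
2. In 3.1 the 6-month re-test is called for below 5 mIU/mL, but the next sentence judges that repeat against 5 mIU/L.
3. A gate of 5,000–10,000 mIU/L would exclude every child whose TSH still lay in the inclusion range.

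All three point to mIU/L.

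**What a unit change alone leaves behind.** Section 9.1.1 would read as above 5 mIU/L with no upper limit, unlike the other statements of the gate. Section 9.4.3 would keep a greater-than sign in front of a 5–10 range. Section 6.3 would keep its limits of above 10 and below 5 with no unit.

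**The case against.** The strongest reply is that this is a slip of the pen that no site would act on. The trigger and the wording of the withdrawal step fix its meaning, 3.1 defines the gate, and no calculation in the plan uses these values. That stands, and it is why the point ranks low.

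It is also fair that safety does not rest on one sentence. Section 4.6 lets the investigator withdraw a child for safety. Section 9.4.1 requires the parent, guardian or primary care provider to be told of clinically relevant abnormal TSH. Section 9.4.2 adjusts the dose for an elevated TSH and repeats the test in 6 weeks. The investigators see TSH results as soon as they are available, and 5.1.1.1 names a single laboratory for the assay. Dose adjustment does not help a child on placebo, but the other provisions do.

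A reader might infer that the withdrawal rule is disabled, so that children with confirmed TSH above 10 would stay on placebo, or that nobody could be randomised. The documents do not support this: the intended limits can be recovered from the text, and the provisions above apply in any case.

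A reader might instead put it down to PDF conversion, since a lost micro sign would explain it: 10 µIU/mL equals 10 mIU/L. That cannot be wholly excluded. However, the radiation paragraph of 9.4.2 keeps its micro sign, the insulin unit in 5.1.1.1 is typed as uIU/mL, and the transposed letters in 6.1.1 look like an authoring slip. Either way, the remedy is one unit throughout.

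**Conclusion.** The error is real and sits in current text: 12 TSH entries in ten places carry a unit 1000 times too large, and they touch four decision rules. It is a unit error, not a miscalculation. The on-study withdrawal step deserves attention first because it is a safety action with no correctly printed version elsewhere.

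Practical impact is low. This rests on sites reading the limits in context, as the document's own definition and triggers invite them to do. Nothing in the sample size, power or analysis sections depends on the unit, so the point should not be read as casting doubt on them. It is a low-priority correction that is worth making because the limits govern randomisation and withdrawal.

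**What to change.** Print mIU/L for every TSH limit, in this order:

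1. In 9.4.2, change the withdrawal step so that the repeat TSH remains above 10 mIU/L.
2. Make the same unit change in 3.1 (two entries), 3.1.2, 3.1.3 and 4.3.1, and in the restatements in the Synopsis, 6.3 and 9.4.3. Correct the misspelt unit in 6.1.1.
3. In 9.1.1, also restore the upper limit so that the gate reads 5–10 mIU/L.
4. In 9.4.3, replace the malformed range with 5–10 mIU/L.
5. In 6.3, add mIU/L to the limits of above 10 and below 5.

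Leave the insulin unit in 5.1.1.1 (uIU/mL) alone; it belongs to a different analyte. The cost is a text correction in a routine amendment, with no change to visits, assays, sample size or analysis.

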9.4.3 Potential Benefits of Trial Participation

There may be no direct benefit and benefits will be to future patients, science, or society. The significant direct potential benefit from participation in this trial would be that subjects found to have subclinical hypothyroid disease (elevated TSH >5-10 mIU/mL) will be treated with levothyroxine. If a subject's TSH is > 10 mIU/L during the observation period, a repeat TSH test will be done within 1-2 weeks. If the repeat TSH is >10 mIU/mL, the thyroid dysfunction will not be considered subclinical and the subject will be referred to an endocrinologist for definitive therapy. Participants may indirectly benefit from identification of abnormalities such as diabetes, dyslipidemia, and hypothyroidism from the fasting blood draw. If clinically relevant abnormalities are found, the family will be notified. With the consent from the family, clinically relevant tests results will be shared with the subject's primary care physician. Only studies performed by CLIA certified labs will be disclosed. Participants found to have an impaired fasting glucose will be referred appropriately for further management and treatment.

9.4.4 Risk-Benefit Assessment

The benefits to participation in this trial outweigh the potential risks. Levothyroxine is used in treating subclinical hypothyroidism with few side effects.

9.5 Recruitment Strategy

Subjects from the corresponding study, IRB #9233 who consent to be screened for this study (IRB #9578) may be recruited if they meet eligibility criteria based on the information collected at the #9233 study visit. Subjects may also be recruited from CHOP's Pediatric Research Consortium (PeRC) and Recruitment Enhancement Core, the CHOP Clinical Research Finder, CNMC Primary Care sites, Endocrinology and Trisomy 21 Clinics, Cardiology Clinics, DS community events, other studies, and through local advertisements. The NIH DS-Connect recruitment will e-mail registry participants the IRB-approved recruitment flyer.

9.6 Informed Consent/Assent and HIPAA Authorization

For subjects recruited from IRB #9233:

The first #9578 visit for these subjects recruited from IRB #9233 will be Blood Draw Visit A. Prior to Blood Draw Visit A, verbal consent from the parent/guardian/legal authorized representative will be obtained and documented by the study coordinator/study investigator. A description of the procedures involved in Blood Draw Visit A, as well as the risks/benefits, will be provided verbally as part of this process. Additionally, it will be stressed that any questions are appropriate and that all aspects of the study are voluntary. Assent may not be obtained for screening purposes if the child subject is not available at the time of the phone call or is not cognitively able.

If the subject is eligible to continue to Study Visit #2, written informed consent for the entire study will be obtained prior to conducting Study Visit #2 procedures. The written informed consent process will be the same as described below for subjects who are not recruited from IRB #9233.

For subjects not recruited from IRB #9233:

Subjects not recruited from IRB #9233 will have an initial telephone screening interview; those who are eligible based on the study inclusion/exclusion criteria will be invited to participate.

Prior to conducting the screening interview, verbal consent from the parent/guardian/legal authorized representative will be obtained and documented by the study coordinator/study investigator. A description of the procedures involved in the study, as well as the risks/benefits will be provided verbally as part of this process. Additionally, it will be stressed that any questions are appropriate and that all aspects of the study are voluntary. Assent may not be obtained for screening purposes if the child subject is not available at the time of the phone call or is not cognitively able.

Prior to conducting the study visit procedures, written informed consent will be obtained from the parents/guardians of children and adolescents with DS. Assent will be obtained from children who, by parent report, are at a first grade or 6 year level of development or higher. . Study participants will be shown a picture book that depicts the study visit and at-home procedures. If the study participant is able to communicate that they understand the procedures, then written assent will be obtained if the participant is able to write, and verbal assent will be obtained if they are not able to write. Assent will not be obtained from subjects who do not have sufficient capacity.

The consent/assent process will take place in a private consent room. It will be stressed again that participation in the study is voluntary and that any questions can and should be raised. Consent and assent will be documented by the parent/guardian/participant's signatures on the approved consent documents. A description of the procedures involved in the study, as well as the risks and benefits, will be provided verbally as part of the consent process.

Consent/assent documents will be maintained in the participant's study file and documented. The parent/guardian will receive a copy of the signed document(s).

9.6.1 Consent for Down syndrome subjects 18 – 20 years of age

For the screening and telephone verbal consent processes, consent will not be obtained for Down syndrome subjects 18-20 years of age.

Consent will be obtained from Down syndrome subjects aged 18-20, when possible, during the in-person written informed consent process that will occur at either Study Visit #1 or Study Visit #2. Ability to provide consent will be ascertained by the study team. Initially, the team will assess the participants' ability by engaging them in conversation to obtain a brief, general sense of their ability to comprehend and communicate. If ability to provide consent seems likely, the team will then explain the following to confirm that the study participant understands all of the essential elements of the consent form:

- a. The purpose of the research study. We will explain that the study is trying to understand if thyroid pill treatment will help improve the health of children
-

and adolescents who have DS and SCH. We will ask them to explain in their own words what the study is about.

- b. Study procedures will be explained with the aid of a picture book that depicts the study visit and at-home procedures. We will then ask them to explain in their own words what each procedure will be like.
- c. The staff will clearly explain that the study participant does not have to participate in the study, that they can change their mind about being in the study at any time, and that no one will be disappointed, upset or consider it a failure if they decide they do not want to continue with the study. Subjects will be asked to explain in their own words that they understand that they do not have to participate in the study and that there are no consequences if they choose not to.
- d. We will explain that their information will be kept private to the best of our ability. We will explain the risks of each procedure. We will also explain that they may learn more about their health from the study, and that their health may improve from taking the thyroid hormone pills, but that it is also possible that they may not benefit from the study. Participants will be asked to explain in their own words what they understand about the risks and benefits of the study.

If it is deemed by the study team at any of the above points that the subject is unable to consent for themselves, the subject's legally authorized representative/health care representative will provide the written informed consent on the subject's behalf.

Assent Procedures

Assent will be obtained and documented on the consent form for children capable of assenting. DS subjects age 18-20 years of age that are not capable of consenting for themselves will have assent documented in the consent form. If the capability of some of the participants is limited in comprehending the study and that they cannot reasonably be consulted, assent will not be obtained in these cases; the investigators will document it on the consent form. Investigators will obtain assent whenever possible.

9.6.2 Waiver of Documentation of Consent

Waiver of documentation of consent is being sought for screening procedures, as the parent/guardian/legal authorized representative may be contacted by telephone and obtaining a signature will not be feasible. As described in (9.6), verbal consent will be obtained and documented by the study coordinator/study investigator prior to conducting the screening interview.

9.6.3 Waiver of Assent

Waiver of assent is being sought for screening procedures, as subjects may not be present when parents/guardians/legally authorized representatives are contacted

9.7 Payment to Subjects/Families

All study procedures and expenses will not be billed to the participant. The total compensation can be up to \$815 for the entire study.

Study Visit #1 (0 month): The total reimbursement for Study Visit #1 is \$150. The parent/guardian will receive a total of \$100 in a pre-paid bankcard to offset the burdens of transportation/parking/time off work/babysitting fees/meals. The bankcard will be loaded with \$50 immediately after the study visit and with an additional \$50 once all post-visit procedures are complete. The participant will receive a \$50 gift card for their efforts toward the study.

Blood Draw Visit A (3 month): For Blood Draw Visit A, the subject will receive \$25 in a pre-paid bankcard for their time and efforts.

Study Visit #2 (6 month): The total reimbursement for Study Visit #2 is \$105. The parent/guardian will receive a total of \$75 in a pre-paid bankcard to offset the burdens of transportation/parking/time off work/babysitting fees/meals. The bankcard will be loaded with \$50 immediately after the study visit and with an additional \$25 once all post-visit procedures are complete. The participant will receive a \$25 gift card plus a small gift worth \$5.00 for their efforts toward the study.

Blood Draw Visit B (7.5 month): For Blood Draw Visit B, the subject will receive \$25 in a pre-paid bankcard for their time and efforts.

Study Visit #3 (12 month): The total reimbursement for Study Visit #3 is \$105. The parent/guardian will receive a total of \$75 in a pre-paid bankcard to offset the burdens of transportation/parking/time off work/babysitting fees/meals. The bankcard will be loaded with \$50 immediately after the study visit and with an additional \$25 once all post-visit procedures are complete. The participant will receive a \$25 gift card plus a small gift worth \$5.00 for their efforts toward the study.

Blood Draw Visit C (13.5 month): For Blood Draw Visit C, the subject will receive \$25 in a pre-paid bankcard for their time and efforts.

Study Visit #4 (18 month): The total reimbursement for Study Visit #4 is \$105. The parent/guardian will receive a total of \$75 in a pre-paid bankcard to offset the burdens of transportation/parking/time off work/babysitting fees/meals. The bankcard will be loaded with \$50 immediately after the study visit and with an additional \$25 once all post-visit procedures are complete. The participant will receive a \$25 gift card plus a small gift worth \$5.00 for their efforts toward the study.

Additional TSH & T4 Checks: In the case of dose adjustments or TSH >10, subjects will receive \$25 in a pre-paid bankcard for each time they have their blood drawn to check TSH and/or T4 levels. Up to 3 TSH and T4 checks may be necessary in the event of dose adjustment(s) or TSH > 10. Subjects will receive up to \$75.00 for these TSH & T4 checks.

In rare circumstances, participants may not be able to complete all study procedures on the date of their study visit (for example, if a machine is broken). If this occurs, we would like to compensate the parent/guardian with an additional \$50 in a bankcard. This additional compensation will be an option for the 4 study visits.

